**AEs are not required to be reported unless they meet SAE criteria.**

Adverse events for Terbium are expected to be nausea (30-40%), vomiting (25-30%). Other common adverse events may include fatigue or asthenia and diarrhoea. Grade 3 or 4 neutropenia, thrombocytopenia, and lymphopenia may be seen in 1%, 2%, and 9% of patients respectively.

**Adverse event management:** All adverse events will be managed as per institutional standards in concordance with gastrointestinal disease management group.

**SAE reporting:** All SAE will be reported within 24 working hours to the IEC, follow up will be given within 14 days and a final SAE will be submitted at resolution of the SAE.

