**Secondary:**

- To assess the safety profile expressed in terms of incidence of >grade 3 toxicity or proportion of patients developing > grade 3 in metastatic neuroendocrine tumors who have progressed on Lu-177 DOTATATE PRRT.

**3. Study End-point:** Safety and efficacy assessment**4. Study Design:** Phase II (Simon Two Stage), Interventional, Single Arm, Open Label**5. Study Sites:** Departments of Nuclear Medicine, TMH, Parel and RRU, ACTREC**6. Pre-screening:** Patients of metastatic NET who have progressed on Lu-177

DOTATATE PRRT will be referred after discussion in Neuroendocrine Tumor Clinic, TMH or HPB-UGI Clinic at RRU, ACTREC.

**7. Screening:** Patients will be confirmed for disease progression on Ga-68 DOTATATE and/or FDG PET/CT imaging.**8. Inclusion Criteria:**

- Male or female, age greater than 18 years
- Histopathological diagnosis of well-differentiated GEP-NET
- Positive Ga-68-DOTANOC PET/CT, Krennigs score  $\geq 3$
- Locally advanced/inoperable disease or metastatic disease
- Patient who have shown disease progression with Lu-177 DOTATATE PRRT

- Karnofsky performance-status score of at least 60 or ECOG performance status </=2
- Life expectancy greater than 6 months

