**15. Study Assessments:**

**Response assessment:** Disease control rate will be measured as a primary endpoint. It is percentage of patients achieving complete or partial response or stable disease on Ga-68 DOTATATE PET/CT. Response assessment will be done using RECIST 1.1 for solid tumors. Non-PD (non-disease progression) after one session of Tb-161 therapy will be eligible for the second session. Patients showing CR with no

residual measurable disease will not undergo a second session of therapy. Patients with PD after 1 cycle of Tb-161 DOTATATE therapy will not continue in the study and will be referred to NET Clinic for further management. Currently there is no standard of care for treatment of refractory NET.

**Safety Assessment:** At each visit, the investigator will evaluate the subject to determine whether any AEs have occurred. CBC, LFT, RFT, Serum electrolytes will be done at 2 weeks, 4 weeks and 6 weeks after each therapy. AEs may be directly observed, reported spontaneously by the subject or by questioning the subject at each study visit. All laboratory values will be evaluated by the Investigator as to clinical significance. All post-baseline abnormal laboratory values considered clinically significant by the Investigator will be recorded as an AE. The NCI Common Terminology Criteria for Adverse Events version 5 (NCI CTCAE v5.0) will be used to classify and grade the intensity of adverse events during and after each treatment cycle. CTCAE will be used to grade all events regardless of attribution, in order to ensure objective reporting, and in order to report trial data according to accepted international guidelines. The highest grade of each observed toxicity will be recorded. The results will be computed in a tabular form in which the proportion of people having their highest grade of toxicity will be charted.

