#### **17. Documentation and archives:**

All patient-related data are recorded in a pseudonymized way. Each patient is unequivocally identified by a trial subject number, attributed at recruitment into the study. The investigator will keep a complete patient identification log, including the full name, address etc.

Patients who were screened in order to be entered into the study, but who could not be recruited for whatever reason will be recorded in a "patient reject log" with the reason for non-inclusion in study being specified. All the data retrieved during the conduct of the study are entered into the case record forms (CRF) by the investigator or co-investigator. All relevant forms and study documents including CRFs will be stored for 10 years at PI place with access to IEC, PI and designated personnel.

**18. Financing of study:** Budgeting details have been provided at the end of study protocol

**19. General ethics for the conduct of the study:** The study will be conducted in compliance with the ICMR Statement on Human Experimentation, and the Declaration of Helsinki principles.

**Declaration of Helsinki:** The trial will be performed in accordance with the Declaration of Helsinki, as decided upon by the 18th World Medical Assembly, Helsinki, Finland, June 1964 (amended by subsequent World Medical Assembly Somerset West, South Africa, October 1996.).

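### Section 15's SAE-only reporting sentence names no recipient, and laboratory values count as AEs only on investigator judgement, so high-grade toxicity could be missed in the only listed secondary endpoint

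*Protocol*

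**What the plan says.** The only secondary objective listed in section 2 is safety, expressed as "incidence of >grade 3 toxicity or proportion of patients developing > grade 3".

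The Safety Assessment part of section 15 describes how toxicity is collected. AEs are sought at each visit, and blood tests are taken 2, 4 and 6 weeks after each therapy. On laboratory findings it says: "All post-baseline abnormal laboratory values considered clinically significant by the Investigator will be recorded as an AE". On grading: "CTCAE will be used to grade all events regardless of attribution, in order to ensure objective reporting". On recording: "The highest grade of each observed toxicity will be recorded". The results are then tabulated so that "the proportion of people having their highest grade of toxicity will be charted".

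Directly after this comes a bold statement: "AEs are not required to be reported unless they meet SAE criteria". It does not say to whom. The text that follows gives expected rates of grade 3 or 4 neutropenia, thrombocytopenia and lymphopenia (1%, 2% and 9%). It then describes, under a label of its own, how SAEs go to the IEC. Section 17 adds that the data retrieved in the study are entered in the CRF. The protocol defines neither SAE nor what it means for an AE to be reported.

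**The concern.** The safety endpoint is a proportion defined by CTCAE grade. Seriousness is a different classification, so a rule that depends on seriousness cannot safely govern which events feed an endpoint that depends on grade. A high-grade blood count found at a scheduled visit need not be an SAE.

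Two routes could lose events:

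- **The bold sentence.** It is unqualified, so site staff could take it as permission not to enter non-serious AEs. The study runs at two sites, which could apply it differently.
- **The clinical-significance condition.** CTCAE is applied to adverse events, and a laboratory abnormality becomes one only on the investigator's judgement. A grade 3 or 4 value judged not significant has no assured path into the tabulation.

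Both routes push the toxicity proportion downward. Safety is half of the study's aim, and all patients have already received Lu-177 PRRT. The protocol cites only four patients treated with Tb-161 in this class of therapy (two in the first-in-human report, two on compassionate use at the institution), so this trial's count will add substantially to the experience it draws on.

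**Working it through.** The protocol gives no figure of its own on this point to reproduce. The check is a comparison of the text, followed by a gauge of how many patients could be affected.

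**Text, side by side**

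| Step | What section 15 requires | Depends on seriousness? | Depends on investigator judgement? |
|---|---|---|---|
| Turning a laboratory value into an AE | Only if judged clinically significant | No | Yes |
| Grading | All events, whatever the attribution | No | Not stated |
| Recording | Worst grade of each observed toxicity | No | Not stated |
| Tabulating | Patients by worst grade | No | Not stated |
| Reporting AEs | Only if SAE criteria are met; recipient not named | Yes | Not stated |

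The last row is compatible with the others only if reporting means something other than capture for analysis. The grading sentence uses the same word for trial data, since it gives objective reporting as the purpose of grading all events. The text therefore does not settle which meaning applies. Restricting the last row to the IEC would leave the condition in the first row untouched.

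**How many patients**

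Inputs: grade 3 or 4 rates of 1% (neutropenia), 2% (thrombocytopenia) and 9% (lymphopenia), from section 15; N = 20 if both stages complete, from section 16.

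- Expected patients, N × p: neutropenia 20 × 0.01 = 0.2; thrombocytopenia 20 × 0.02 = 0.4; lymphopenia 20 × 0.09 = 1.8.
- Patients with at least one of the three. With complete overlap the rate is the largest of the three, 9%: 20 × 0.09 = 1.8. With no overlap it is 0.01 + 0.02 + 0.09 = 12%: 20 × 0.12 = 2.4. Under independence it is 1 − 0.99 × 0.98 × 0.91 = 11.7%: 20 × 0.117 = 2.3.
- Chance that at least one patient has such an event: 1 − 0.91^20 = 84.8% at 9%, and 1 − 0.88^20 = 92.2% at 12%. This is the chance that an event occurs, not that it goes unrecorded.

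**How many could be lost**

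Let s be the share of these patients whose events are not captured, because they are non-serious (strict reading) or judged not clinically significant (either reading). The loss is s × (1.8 to 2.4) patients. The protocol gives no value for s:

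- s = 0: no loss.
- s = 1: 1.8 to 2.4 patients, or 9 to 12 percentage points of the grade 3 or 4 proportion.

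These figures are for grades 3 and 4 combined. The objective is written as strictly above grade 3, which taken literally leaves grade 3 out whatever the reporting rule. The protocol gives no separate grade 4 rate, so the loss from the literal endpoint cannot be sized.

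**The case against.** The strongest reply is that recording and reporting are different acts. Section 15 requires the worst grade of each toxicity to be recorded, with no condition on seriousness, and section 17 sends the retrieved data to the CRF. The only AE reporting route described is for SAEs to the IEC. Read that way, the bold sentence merely spares the IEC non-serious events, and the passages agree.

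Much of this stands. The IEC reading is available and may well be what was meant. A reader might infer that section 15 certainly contradicts itself, that most grade 3 laboratory toxicity would be omitted, or that the trial would report no events in 20 patients. The protocol does not support these inferences: they need the strict reading plus a figure for the non-serious share, which it does not give. Grade 3 events are also outside the objective as literally worded.

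The reply does not remove the point. The bold sentence is not placed under the SAE-reporting label and names no recipient. Section 17 covers data that have been retrieved but does not say that non-serious AEs must be.

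It can also be said that investigator judgement on laboratory AEs is stated openly and is a matter of preference. It does not conflict with the bold sentence. But it lets an endpoint defined by objective grade depend on an ungraded opinion, and the IEC reading does nothing about that. The requirement to record each observed toxicity might be thought to cover such values, but the protocol does not say that a value judged not significant is still a toxicity.

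**Conclusion.** The point holds in conditional form. The bold sentence is ambiguous and conflicts on its face with the plan to grade, record and tabulate all events. Read as a capture rule, it could bias the only listed secondary endpoint downward. Separately, and under either reading, the clinical-significance condition could leave a grade 3 or 4 laboratory value uncounted.

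The number at risk is 1.8 to 2.4 of 20 patients, and the actual loss could be anywhere from none to all of them. This rests on the protocol's own expected rates, on accrual of all 20 patients, and on taking the endpoint to include grade 3. No sample size, power or decision rule for the primary endpoint is affected. The change should be made before enrolment, because events not captured at the time may not be recoverable.

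**What to change.** 1. Replace the bold sentence in section 15 with one limited to the IEC, for example: *Non-serious AEs do not need expedited reporting to the IEC.*
2. Add a capture rule, for example: *All AEs and all scheduled laboratory values are graded by CTCAE v5.0, recorded in the CRF and counted in the safety endpoint, whatever their seriousness or judged clinical significance.* The investigator's view of clinical significance can still be noted alongside the grade.
3. In section 2, state whether grade 3 counts towards the objective, and bring that wording into line with the grade 3 or 4 rates in section 15.

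The cost is a few sentences and slightly more CRF entry; the blood tests are already scheduled. The toxicity rate may look less favourable than under a narrower capture rule. If IEC reporting was all that was meant, the first change only says so.

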#### **16. Statistical Analysis for sample size calculation:**

At the end of the study, we expect a disease control rate (DCR) of 87% in patients with metastatic NET progressed after Lu-177 DOTATATE PRRT.

Baseline assumption is DCR of 67% from historic control and addition of Terbium-161 DOTATATE therapy will improve DCR by 20%. The null hypothesis will be tested against a one-sided alternative with type I error rate of 0.05 & power of 0.80 in standard Simon two stage design. In the first stage, 6 patients will be accrued. If there are <4 responses, the study will be stopped. Otherwise, 14 additional patients will be accrued for a total of 20. The null hypothesis will be rejected if =/≥ 16 responses are observed in 20 patients.

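### The two-stage rule in Section 16 (6 then 20 patients, success at 16 or more) has a one-sided type I error of 0.152, not the stated 0.05

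*Protocol*

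**What the plan says.** Section 4 of the Protocol describes the trial as "Phase II (Simon Two Stage), Interventional, Single Arm, Open Label". Section 15 makes DCR the primary endpoint. Section 16 holds the whole design calculation:

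- Null rate: "Baseline assumption is DCR of 67% from historic control". The expected rate is 87%, a gain of 20 percentage points.
- Error rates: "The null hypothesis will be tested against a one-sided alternative with type I error rate of 0.05 & power of 0.80".
- Stage 1: "In the first stage, 6 patients will be accrued. If there are <4 responses, the study will be stopped".
- Stage 2: 14 further patients, for a total of 20.
- Final rule: "The null hypothesis will be rejected if =/≥ 16 responses are observed in 20 patients".

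No other section restates or modifies this rule.

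**The concern.** The two response rates, the two sample sizes and the two cut-offs fully determine the type I error and power of a two-stage binomial design. Section 16 gives all of them, so its claim of 0.05 and 0.80 can be checked exactly. A separate analysis plan could not make the claim true if it fails.

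The cut-off looks low at first sight: 16 of 20 is 80%, only 13 points above the 67% null, and 20 patients give little precision. If the true type I error is well above 0.05, a final count at or just above the cut-off would be reported as significant at one-sided 5% when it is not. The primary conclusion would then rest on a false error rate.

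**Working it through.** **Inputs (all from Section 16).** p0 = 0.67; p1 = 0.87; stage 1 n1 = 6, continue if X1 ≥ 4; stage 2 n2 = 14; reject if X1 + X2 ≥ 16.

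**Formula.** P(reject | p) = Σ over x = 4, 5, 6 of P(X1 = x | 6, p) × P(X2 ≥ 16 − x | 14, p).

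**Rule as printed.**

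| x | P(X1 = x), p = 0.67 | P(X2 ≥ 16 − x), p = 0.67 | product | P(X1 = x), p = 0.87 | P(X2 ≥ 16 − x), p = 0.87 | product |
|---|---|---|---|---|---|---|
| 4 | 0.3292 | 0.1101 | 0.0362 | 0.1452 | 0.7292 | 0.1059 |
| 5 | 0.2673 | 0.2699 | 0.0721 | 0.3888 | 0.9021 | 0.3507 |
| 6 | 0.0905 | 0.4862 | 0.0440 | 0.4336 | 0.9731 | 0.4220 |
| Sum | | | **0.1524** | | | **0.8786** |

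(The sums are taken before rounding.) The stated 0.05 and 0.80 are not reproduced. The ratio is 0.1524 / 0.05 = 3.05, and 1 / 0.1524 = 6.6, so there is about one false success in 6.6 trials under the null.

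**Early stopping.** P(X1 ≤ 3 | 0.67) = 0.313. Expected sample size under the null is 6 + 14 × (1 − 0.313) = 15.6. Under p = 0.87 the stopping probability is 0.032.

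**Other readings of the cut-offs, 20 patients.**

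| Stop in stage 1 | Reject | Type I error | Power |
|---|---|---|---|
| ≤3 of 6 (as printed) | ≥16 (as printed) | 0.152 | 0.879 |
| ≤4 of 6 | ≥16 | 0.116 | 0.773 |
| ≤3 of 6 | ≥17 | 0.063 | 0.739 |
| ≤4 of 6 | ≥17 | 0.054 | 0.675 |
| ≤3 of 6 | ≥18 | 0.019 | 0.508 |
| ≤4 of 6 | ≥18 | 0.018 | 0.487 |
| no interim stop | ≥16 | 0.159 | 0.892 |

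None gives both stated figures. Taking the 20% as a relative gain would change power only, because the type I error depends on the 67% null alone. It would also contradict the stated 87%.

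**Null rate at which the printed rule would hold 0.05.** The type I error is 0.0403 at p0 = 0.59, 0.0486 at 0.60 and 0.1131 at 0.65. The rule therefore fits a null of about 60% or lower, not 67%.

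**What 67% against 87% requires.** Enumerating all two-stage designs with one-sided type I error ≤0.05 and power ≥0.80:

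- N ≤ 27: none.
- Minimax: stop if ≤18 of 23, N = 28, reject at ≥23 (0.048 / 0.802).
- Optimal: stop if ≤7 of 10, N = 32, reject at ≥26 (0.046 / 0.807).
- N = 20, best power with error ≤0.05: stop if ≤11 of 14, reject at ≥17 (0.0497 / 0.668).

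**Supporting check.** For 16 of 20, the exact one-sided 95% lower bound (Clopper–Pearson) is 0.599, below 0.67. This is a single-stage bound that ignores the interim stop, so it only supports the two-stage calculation.

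**The case against.** The strongest defence is that a one-sided error near 0.15 can be tolerated in a small, exploratory single-arm phase II trial, and that the rule has more power than claimed (0.879 against 0.80). Both points are fair, but they argue for declaring 0.15, and the Protocol declares 0.05. The extra power comes from the lenient cut-off.

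Several limits on the concern do stand:

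- The null is a rate equal to historic control. It does not describe a treatment without activity, so the false-positive risk is that of claiming an improvement over 67% when there is none.
- The false claim of 5% significance attaches to final counts of 16 or 17. With the same stage 1, rejecting at 18 or more has an error of 0.019, so such a result would meet 0.05.
- Changing a cut-off or the stage 1 size is more than a wording change. Section 21 requires a formal amendment for changes to study design or sample size.

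None of these restores the stated error rate.

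**Conclusion.** The concern holds and must be fixed. The rule in Section 16 has a one-sided type I error of 0.152 and power of 0.879, against the stated 0.05 and 0.80. The result rests on the Protocol's own figures and on independent binary outcomes in exactly 6 and then 20 evaluable patients, with the stage 1 stop followed. No outside assumption enters. The stated error rates, the 67% null and the 6/20/16 rule cannot all be true together, and 20 patients cannot deliver 0.05 and 0.80 for 67% against 87% under any two-stage cut-offs.

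**What to change.** Remove the claim that 20 patients give 0.05 and 0.80, and adopt one of the following before outcomes are known:

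1. **Keep the rule and state its true properties:** one-sided type I error 0.15, power 0.88. This changes text only and adds no patients. The cost is a less favourable stated error rate, and a result of 16 or 17 of 20 may not be described as significant at 5%.
2. **Keep 20 patients and hold 0.05:** stage 1 of 14 (stop if 11 or fewer), reject at 17 or more of 20, and state type I error 0.050 and power 0.67. The cost is lower power and a later futility look, after 14 patients instead of 6.
3. **Keep 20 patients and the present stage 1:** reject at 18 or more and state type I error 0.019 and power 0.51. This preserves the early look at 6 patients but has less power than option 2.

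If both 0.05 and 0.80 are to be kept, the design needs at least 28 patients (minimax), or 32 with the optimal design; that is 8 to 12 more than planned.

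Option 1 is the cheapest. Options 2 and 3 and any increase in sample size need a formal amendment submitted to the ethics committee under Section 21.

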#### **17. Documentation and archives:**

All patient-related data are recorded in a pseudonymized way. Each patient is unequivocally identified by a trial subject number, attributed at recruitment into the study. The investigator will keep a complete patient identification log, including the full name, address etc.

Patients who were screened in order to be entered into the study, but who could not be recruited for whatever reason will be recorded in a "patient reject log" with the reason for non-inclusion in study being specified. All the data retrieved during the conduct of the study are entered into the case record forms (CRF) by the investigator or co-investigator. All relevant forms and study documents including CRFs will be stored for 10 years at PI place with access to IEC, PI and designated personnel.

**18. Financing of study:** Budgeting details have been provided at the end of study protocol

**19. General ethics for the conduct of the study:** The study will be conducted in compliance with the ICMR Statement on Human Experimentation, and the Declaration of Helsinki principles.

**Declaration of Helsinki:** The trial will be performed in accordance with the Declaration of Helsinki, as decided upon by the 18th World Medical Assembly, Helsinki, Finland, June 1964 (amended by subsequent World Medical Assembly Somerset West, South Africa, October 1996.).

**20. Informed consent:** The Investigator or a person designated by him/her will collect informed consent from all participants, prior to which the Investigator or co-investigator must inform each participant of the objectives, benefits, risks and requirements of the study. He/she will also provide the participant with an information sheet in clear, simple language. The study participant will be allowed ample time to inquire about details of the study and to decide whether or not to participate in the study. Moreover, the patient will receive a written "patient information", containing all relevant information for the patient's decision and the course of the study. The consent of the patient to participate must be obtained in writing before recruitment into the study. The informed consent form must be dated and signed by the patient. Thereby, he declares his voluntary consent to participate in the study and his willingness to comply with the requirements of the trial and the instructions of the treating investigator during the course of the study. There are two copies of the informed consent form: one for the patient and one to be kept by the investigator in his study documents. The informed consent is only valid after receiving the patient's signature. Thereafter, the patient can be entered into the study if he/she fulfills the selection criteria. The study will not commence until approval has been obtained from the Tata Memorial Hospital Human Ethics Committee.

**21. Protocol amendments:** Any modifications to the protocol which may impact on the conduct of the study, potential benefit of the study, or may affect patient safety, including changes of study objectives, study design, patient population, sample sizes, study procedures, or significant administrative aspects will require a formal amendment to the protocol. Such amendment will be agreed upon by the investigators and then submitted to the IEC/IRB for acceptance.

Administrative or technical changes of the protocol such as minor corrections and/or clarifications that have no effect on the way the study is to be conducted, nor on the risk-benefit ratio, will be agreed upon by all the investigators and will be documented in a memorandum to the protocol. The IEC may be notified of such changes at the discretion of the sponsor/coordinating investigator. The coordinating investigator has to assure, that all amendments have been added to the study documents at any site involved in the trial.

**22. Reimbursement:** The study budget shall include costs of blood investigations and imaging studies, Tb-161 therapy and post-therapy dosimetry scanning. Patients study visits will also be budgeted in the study.

**23. Compensation:** It will be as per the Institutional IEC policy

**24. Evaluation of Benefits and Risks/Discomforts:** There is potential benefit in the form of improved survival and quality of life from this study. No potential physical, psychological or social risks. There are no alternate treatment possible during the study

**25. Risks/Benefits Analysis:** The study poses minimal risk, i.e. the probability and magnitude of harm or discomfort anticipated in the research are not greater in and of themselves than those ordinarily encountered in daily life or during the performance of

routine physical or psychological examinations or tests.

**26. Consent and Assent Process and Documentation:** Consent shall be taken after giving adequate time to the patient and Legally Accepted Representative to understand the study design. Consent shall be signed and dated by the patient and countersigned by the investigator. **A copy of the consent shall be handed over to the patient and one copy shall be kept for records.** Impartial witnesses shall be present to overlook the consent administration process. Participants' right to refuse to participate in the trial shall be respected. After the participant has entered into the trial, the clinician shall give alternative treatment to that specified in the protocol, at any stage, if he/she feels it to be in the best interest of the participant. The reason for doing so, shall be recorded; the participant will remain within the trial for the purpose of follow-up and for data analysis by the treatment option to which they have been allocated.

Similarly, the participant must remain free to change their mind at any time about the protocol treatment and trial follow-up without giving a reason and without prejudicing his/her further treatment. Patients who are not able to give consent won't be included in the study. In case a patient loses his/her ability to give consent during the study, he/she will be dropped out of the study.

**27. Trial closure:** The trial will close when all patients have completed follow-up. Details about reporting of trial closure to the regulatory and ethical committees.

**28. Dissemination Of Results:** The trial results will be submitted for publication in international peer reviewed journals and presented at national/international conferences. No publication restrictions will be imposed by trial sponsors. The contribution of all investigators will be acknowledged in such manuscripts if they are not eligible for authorship. In addition the grant giving organizations will also be acknowledged in all publications.

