- c.** Clinical and Quality of Life Assessment using EORTC QLQ C30 questionnaire before therapy, at 4 weeks and 8 weeks after each therapy session.
- d.** Imaging Follow-up (as per established institutional standard-of-care) as follows: Ga-68 DOTANOC PET/CT will be performed at 4-6 weeks after each therapy session for documentation of response. After completion of protocol treatment, patients will be followed up as per standard institutional practices.

**13. Study Duration:** 2 years

**14. Follow-up Period:** 1 year

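### Section 26 allows other treatment at any stage and keeps the patient in the analysis as Tb-161, and nothing restricts other anticancer therapy before the response scan, so disease control after another agent could count as success

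*Protocol*

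**What the plan says.** - **Section 26 (consent).** If judged best for the participant, "the clinician shall give alternative treatment to that specified in the protocol, at any stage". The reason is to be recorded, and the participant stays in the trial for "follow-up and for data analysis by the treatment option to which they have been allocated".
- **Section 15 (response assessment).** Disease control rate (DCR), the primary endpoint, is the percentage with "complete or partial response or stable disease on Ga-68 DOTATATE PET/CT". No condition is set on therapy received before the scan. The same section says "Patients with PD after 1 cycle of Tb-161 DOTATATE therapy will not continue in the study" and that "Currently there is no standard of care for treatment of refractory NET".
- **Sections 10 and 12.** Two cycles are given 8-12 weeks apart, and "PET/CT will be performed at 4-6 weeks after each therapy session for documentation of response". Section 12 also mentions follow-up during cancer-directed therapy. That may mean Tb-161 itself, and it restricts nothing.
- **Section 16.** "Baseline assumption is DCR of 67% from historic control"; the trial continues after stage 1 unless fewer than 4 of 6 respond, and it rejects the null from the point where "16 responses are observed in 20 patients".
- **Section 24 (benefits and risks).** It states that no alternative treatment is possible during the study.
- **Section 17.** All retrieved data go to the case record form (CRF). Agent and dates of other anticancer therapy are not named as items.

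**The concern.** Analysing patients by allocated treatment is a rule from randomised trials, where a control arm is exposed to similar switching. Here there is one arm and a fixed historic rate, so nothing offsets the effect of another agent. Keeping the switched patient in the analysis is right. The gap is that the protocol permits the switch, does not limit other anticancer therapy before the scan, and defines success without regard to it.

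Stable disease counts as success and N is 20, so each patient moves DCR by 1/20 = 5 percentage points. If other therapy is neither restricted nor recorded with dates, its contribution to the observed DCR cannot be separated afterwards.

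**Working it through.** **1. Is there a restriction anywhere?** Sections 8 and 9 (eligibility), 10 (treatment), 11 and 12 (scanning, follow-up) and 15 (assessments) contain no prohibited-therapy, washout or stable-background rule. Section 24 points the other way from section 26, but it describes benefits and risks and does not instruct anyone to withhold therapy.

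**2. When could a switch matter?** Times run from session 1.
- Before the first scan: 4-6 weeks.
- In a non-progressing patient before the scan after session 2: (8 to 12) + (4 to 6) = 12-18 weeks. This applies only if that scan is the endpoint scan, and the protocol does not name it.
- After progression at the first scan: closed, because the patient leaves the study.

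**3. The stated rule.** Continue at 4 or more of 6; reject at 16 or more of 20.

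P(success) = sum over x = 4, 5, 6 of P(X1 = x) × P(X2 ≥ 16 − x), with X1 ~ Bin(6, p) and X2 ~ Bin(14, p).

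At p = 0.67: 0.3292 × 0.1101 + 0.2673 × 0.2699 + 0.0905 × 0.4862 = 0.036 + 0.072 + 0.044 = 0.152. At p = 0.87 the same sum gives 0.879. The first figure does not reproduce the stated type I error of 0.05. That is a separate matter; 0.152 serves here only as the base for comparison.

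The expected count at 67% is 20 × 0.67 = 13.4, which is 16 − 13.4 = 2.6 patients below the boundary.

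**4. Illustration A: m of 20 patients receive another agent.** The protocol gives no switch rate, so m is assumed, as is q, the probability that a switched patient is scored as controlled. The other patients have 0.67, and the m patients fall at random across the two stages. P(success), base 0.152:

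| q | m = 1 | m = 2 | m = 3 |
|---|---|---|---|
| 0.50 | 0.134 | 0.117 | 0.102 |
| 0.67 | 0.152 | 0.152 | 0.152 |
| 0.87 | 0.174 | 0.198 | 0.225 |
| 1.00 | 0.188 | 0.231 | 0.280 |

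The change runs from −0.02 to +0.04 with one patient, −0.04 to +0.08 with two and −0.05 to +0.13 with three. It is zero when switched patients do as well as the rest.

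**5. Illustration B: only patients without progression at the first scan switch.** Let p1 be the probability of no progression at the first scan (assumed 0.75 to 0.90), p2 = 0.67/p1 the probability of later control without a switch, and s the share of these patients who switch.

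DCR = p1 × [(1 − s) × p2 + s × q]; expected switchers = 20 × p1 × s.

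Example: p1 = 0.90, s = 0.10, q = 1.00 gives 0.67 × 0.90 + 0.90 × 0.10 = 0.693, and P(success) = 0.209.

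| s | Expected switchers | P(success), q = 1.00 | P(success), q = 0.87 |
|---|---|---|---|
| 5% | 0.75-0.9 | 0.161-0.179 | 0.151-0.165 |
| 10% | 1.5-1.8 | 0.171-0.209 | 0.149-0.179 |
| 15% | 2.25-2.7 | 0.180-0.242 | 0.147-0.193 |

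On this path the change runs from about −0.01 to +0.09.

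**6. Cost of scoring switched patients as failures.** At a true DCR of 87%, power under the stated rule is 0.879 with none, 0.754 with one and 0.559 with two.

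**The case against.** The strongest case is that this is a welfare clause in a consent section. It keeps patients in the analysis, which is correct, and does not itself say how a response after another agent is scored. That scoring rule is commonly set in the SAP, which is not shown, and an SAP could keep such a patient in the denominator as not controlled without contradicting section 26. Section 24 suggests that the investigators expected no switching, and section 15 says refractory NET has no standard of care. The CRF may already capture agent and dates.

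Most of this stands and limits the point: the protocol leaves open that such disease control could count, and does not decide that it will. It does not remove the point. Who may receive other therapy before the endpoint is a matter of trial conduct and belongs in the protocol. Lack of a standard of care does not mean lack of other treatment, since section 15 refers progressing patients to the NET clinic for further management. A log alone would not settle what counts.

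A reader might infer three stronger things that the document does not support:

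- **That progressing patients could be rescued into successes.** Those with progression after cycle 1 leave the study.
- **That the result will be biased in favour of Tb-161.** No switch rate is given, and the effect can be zero or negative.
- **That section 24 already prohibits other therapy.** It is not written as a rule, and section 26 contradicts it.

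**Conclusion.** The point holds in limited form. As written, sections 15 and 26 together allow disease control seen after another agent to count towards the 16 of 20, and no section restricts such therapy before the response scan. Sections 24 and 26 also conflict. Neither the size nor the direction of the effect can be computed from the protocol. The illustrations rest on assumed switch counts and control probabilities. They show that one to three patients could matter in a trial of 20, not that they will. The second window depends further on which scan is the endpoint scan. This is a cheap improvement worth making before enrolment, not a flaw that by itself invalidates the design.

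**What to change.** 1. **Section 10:** state that no other anticancer therapy may be started or intensified between the baseline scan and the response scan. Allow unchanged background therapy as the investigators define it, and keep the section 26 welfare clause.
2. **Section 24:** reword it to agree with section 26.
3. **CRF:** record the agent and the start and stop dates of any anticancer therapy, at baseline and during treatment, if this is not already done.
4. **Analysis:** keep any patient who still switches in the denominator. Report a sensitivity analysis in which disease control first documented after new therapy is not counted as success. State how this applies to a patient already controlled at the first scan who switches before the second.

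Whether item 4 becomes the primary scoring can be left to the SAP, because each patient scored as a failure lowers the observed DCR by up to 5 points and lowers power as shown above. Items 1 and 3 should be the main safeguard. The cost is one protocol paragraph, one corrected sentence and at most one CRF page, with no change to the sample size.
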